6. SUBJECT RECRUITMENT & SCREENING

This study will have a sample size of 60 adults (males and females) between 20 to 40 years of age. This sample size will provide us with enough power to detect the needed effect size. The estimated attrition rate is 15 percent. The participants will be recruited from the student population at Loma Linda University via flyers, posters, hand-outs, mass emails, and word of mouth. The phone script will be used when potential subjects contact us after seeing the flyer.

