7. INFORMED CONSENT PROCESS

The informed consent will be conducted by [name] in the SAHP Neuroscience Research Laboratory with a single potential subject at a time. Participants will have the opportunity to ask questions before deciding to participate. Those participants who meet inclusion criteria will be identified by a code on all documents other than their signature on the informed consent. Twenty participants with no pain will be in the normal group. Forty participants with chronic subclinical neck or upper quadrant pain will be randomized (random number table will be used) into two groups: twenty subjects in the control group, and twenty subjects in the intervention group. All participants' records will be stored in a locked cabinet, in a locked office and stored on a secure drive.

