- 1) To measure the immediate and short-term effects of TENS on subclinical neck or upper quadrant pain with the VAS, anxiety with the State-Trait Anxiety Inventory for Adults™, disability with neck disability index (NDI), disability and cervical spine proprioception Noraxon 3D Inertial Motion Capture System in subjects 20-40 years of age.
- 2) To measure pain, anxiety, disability, and cervical spine proprioception in subjects with and without neck or upper quadrant pain.
- 3) To compare compliance of TENS home usage in groups with and without short message system (SMS), text message, reminders.

c. Procedures involved (Research Interventions)

There will be three groups as follows: twenty subjects with no pain in the normal group; forty subjects with chronic subclinical neck or upper quadrant pain will be randomized into two groups: twenty subjects in the control group, and twenty subjects in the intervention group. The intervention group will be further randomized into two groups: ten subjects will receive instructions for home use of TENS with daily SMS text message reminders and ten subjects will receive instructions for home use of TENS without SMS text message reminders. We will aim for an equal distribution of males and females in each group.

First session (Day 1): Before starting the procedures, participants complaining of pain that are greater than 4/10 in the VAS will be excluded from the study as this will be greater of what we consider to be subclinical pain based on literature review and if the pain has been present less than three months. In addition, if participants with pain less than 4/10 pain receiving clinical pain treatment, have taken pain medication

within six hours of first session, have acute pain or contraindications for electrical stimulation would be excluded from the study. Following completion of the signing procedures, all participants will be given brief explanations before administration of the questionnaires.

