Data was analyzed using SPSS version 28.0. Assuming a moderate effect size of 0.3, a power of 0.80, an alpha of 0.05 and 15% dropout rate, the estimated sample size was 40 participants. Data was summarized using frequency (%) for qualitative variables, mean \pm standard deviation (SD) for continuous variables, and median (minimum, maximum) when the distribution was not approximately normal. The normality of the outcome variables was examined using the Shapiro wilk test and boxplots. The frequency distribution of gender between the two study groups was compared using Fisher's exact test. Mean baseline characteristics and outcome variables by study group was examined using independent t-test. Median VAS, NDI, and JPE rotation right were compared between the intervention and control groups using Mann-Whitney U test. For each study group, changes in mean outcome variables (cervical spine AROM, anxiety, neck proprioception, VAS, NDI) over time (post versus pre) were examined using paired t-test or Wilcoxon signed rank test when the distribution is not approximately normal. Changes in outcome variables by group (intervention versus control) overtime (post 2 weeks versus pre) were assessed using 2x2 mixed factorial analysis of variance (ANOVA). If there was a significant interaction between group and time, the changes are significantly different between the two groups. There was a significant difference in mean STAI_T and lateral flexion left between the intervention and control groups at baseline, thus this was controlled for baseline differences using analysis of covariance (ANCOVA). In the intervention group, we examined changes in outcome variables over time (pre versus post 30 minutes versus post 2 weeks) using repeated measures ANOVA or Friedman's test if the data was not approximately normal. If the results were significant, Bonferroni's post hoc comparisons were conducted, or Wilcoxon signed rank test were used to determine what times were significantly different. The level of significance was set at $p \leq 0.05$.

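### Equal numbers of males and females in each group are a stated aim, but the plan names no step that would produce them; the cost is lost balance and some precision, not bias

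*Protocol*

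**What the plan says.** Protocol section 8, part c, describes the three groups and the two randomisations, then adds: "We will aim for an equal distribution of males and females in each group".

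The allocation method appears once, in Protocol section 7, where the participants with pain "will be randomized (random number table will be used) into two groups". The planned sizes are "twenty subjects in the control group, and twenty subjects in the intervention group". A second step follows in section 8: "The intervention group will be further randomized into two groups", ten with and ten without text-message reminders. No method is named for that step. The pain-free group is not randomised: "Twenty participants with no pain will be in the normal group".

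Protocol section 6 says that both sexes will be recruited but gives no ratio or quota.

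In the SAP, sex appears in one place: "The frequency distribution of gender between the two study groups was compared", using Fisher's exact test. It is not named as a covariate. ANCOVA is described only for two variables that differed significantly at baseline, trait anxiety and left lateral flexion.

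**The concern.** A design property is stated with no mechanism attached. A random number table used without strata leaves the sex split in each arm to chance, and in arms of 20 and subgroups of 10 chance departures from equality are frequent. The SAP's test looks at the split only after allocation, when it can no longer be changed.

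Two things are at stake. The report may claim or imply sex balance that the method was not built to give. And if sex predicts an outcome, leaving it out of both allocation and analysis gives up a little precision. There is also a practical risk: staff told to aim for balance, without a tool for it, may be tempted to steer assignments in a study where the comparison is stimulation against no intervention and no concealment of the list is described.

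**Working it through.** The plan gives no probability or tolerance for sex balance, so there is no figure of its own to reproduce on this point. The SAP's total of 40 enters only as the number randomised.

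**Inputs.** 40 randomised, 20 per arm (Protocol sections 7 and 8); intervention arm then split 10 and 10 (section 8). Sex mix at recruitment: not given. The best case is assumed to be 20 females and 20 males, with other mixes shown below.

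**Step 1. Exact balance in the two arms, best case.** The number of females in one arm is hypergeometric.
- P(10:10) = C(20,10)² / C(40,20) = 184,756² / 137,846,528,820 = 0.248

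**Step 2. Adding the reminder subgroups.**
- P(5:5 given 10:10) = C(10,5)² / C(20,10) = 63,504 / 184,756 = 0.344
- Both levels: 0.248 × 0.344 = 0.085

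**Step 3. Looser readings, best case.**
- 9 to 11 females per arm: 0.657
- 8 to 12 females per arm: 0.887
- 7:13 or worse: 1 − 0.887 = 0.113

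**Step 4. Other recruitment mixes.**
- If the mix is left to chance, P(10:10 in both arms) is 0.176² = 0.031 at 50% female, 0.014 at 60% and 0.001 at 70%.
- If the aim means only the same split in both arms, the chance is 0.248, 0.252, 0.259 and 0.269 when 20, 24, 26 or 28 of the 40 are of one sex.

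**Step 5. What Fisher's test would flag (20 v 20).**

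| Split | p |
|---|---|
| 12 v 8 | 0.34 |
| 13 v 7 | 0.11 |
| 14 v 6 | 0.026 |

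The first split to reach 0.05 is 14 v 6. If sex were handled as the two imbalanced baseline variables were, a 13 v 7 split would go unadjusted.

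**Step 6. Size of the effect on a comparison of levels.** The variance of the female count in one arm is 20 × 0.5 × 0.5 × 20/39 = 2.56, so its SD is 1.60. The difference in female proportion between arms then has SD 2 × 1.60/20 = 0.16. The standard error of a two-arm difference with 20 per arm is √(2/20) = 0.32 SD. The outcome difference between the sexes is not in the documents, so a range is assumed:

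| Assumed sex difference | Typical (RMS) shift | Shift at 7:13 (0.65 − 0.35 = 0.30) |
|---|---|---|
| 0.25 SD | 0.04 SD | 0.075 SD |
| 0.5 SD | 0.08 SD | 0.15 SD |
| 0.75 SD | 0.12 SD | 0.225 SD |

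At 0.5 SD, the share of sampling variance due to sex imbalance is 0.08²/0.32², about 6%.

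**Step 7. Whether stratification delivers.** With 20 of each sex and blocks that fill exactly at 20 per stratum, 10:10 is certain, and likewise 5:5 if the reminder lists close at 10 per sex. Freely varying blocks do not guarantee it. With sizes 2 and 4 equally likely, the chance that a block ends at the 18th assignment is 0.666, so a block of 4 is cut in half at the 20th with chance 0.666 × 0.5 = 0.333. Half a block of 4 is unbalanced with chance 2/6. Each stratum therefore misses with chance 0.111, and at least one of two misses with chance 1 − 0.889² = 0.21. With sizes 4 and 6 the miss rate is roughly two in five.

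**The case against.** **The wording is an aim, not a guarantee.** If 9 to 11 of each sex per arm is good enough, the table delivers it about two times in three under even recruitment. This stands: a reader might infer that the method usually fails, and that is right only for exact equality. Even on the looser reading it misses about one time in three.

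**Unstratified use is inferred from silence.** A random number table can be used within strata. That is true; the documents do not rule it out. They also describe no strata, blocks or quota, so the reader cannot tell.

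**A reader might infer bias or confounding.** The documents do not support that. Chance imbalance under randomisation has expectation zero and is already part of the standard error. The SAP's main comparison is the group-by-time interaction, and a sex difference that is constant over time cancels from pre-to-post change. The shifts in Step 6 apply only to comparisons of levels (for example the t-tests or Mann-Whitney tests, if used after treatment), or where sex changes the response itself.

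**A reader might infer that balance could be honoured only by overriding assignments by hand.** Not so: randomising within sex honours it and keeps the allocation random.

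**The Fisher test is ordinary description, and the reminder split serves compliance.** Both fair. The test is harmless as description; it just cannot create balance or decide whether to adjust. The SAP lists no outcome comparison between the reminder subgroups, so imbalance there bears on the compliance objective, not on the pain or anxiety results.

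**Conclusion.** The point holds as a mismatch between a stated aim and the stated method. With simple randomisation and the best possible recruitment, exact sex balance in the two arms has a 25% chance, falling to 8.5% with the reminder subgroups and to 3% or less for the two arms if the recruited mix is itself left to chance. A 7:13 or worse split has an 11% chance, and the planned test would not flag 13 v 7.

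The consequence is modest: loss of balance, and of about 6% of sampling variance in a comparison of levels if the sexes differ by an assumed 0.5 SD. It is not a systematic bias and does not threaten the validity of the randomised comparison. The conclusion rests on fixed arms of 20, on reading silence as no stratification, and on the assumed recruitment mix.

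**What to change.** **If allocation is still open**
- In Protocol sections 7 and 8, set a recruitment quota by sex in all three groups. Stratification makes the randomised arms alike, but equal numbers need a quota, and in the non-randomised normal group a quota is the only route.
- Randomise within sex using permuted blocks that close at the planned totals: 10 per arm per sex, then 5 per reminder subgroup per sex. Block sizes can still vary if a fixed set summing to the total is shuffled, for example blocks of 2 and 4 summing to 20, and 4, 4 and 2 summing to 10.
- Keep the lists from the person who recruits.

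**In the analysis, in either case**
- Include sex as a factor in the group comparison regardless of the Fisher p-value. In the mixed ANOVA this means sex together with its interaction with time, since a main effect of sex alone does not touch the group-by-time test.
- Keep the gender table as description only.

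**If allocation is complete**, as the SAP's past tense suggests: report the method actually used, adjust for sex, and do not claim sex balance by design.

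**Cost.** One list per sex at each randomisation instead of one list; one degree of freedom (38 to 37 on change with 40 participants); slower recruitment if one sex is scarce; and somewhat more predictable assignments in an open study. Balance is secured at randomisation only: the planned 15% attrition can still disturb it.

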First, participants in the normal group (20 subjects) will first be instructed to complete the VAS for pain, a subjective measure of pain intensity consisting of a 10 centimeter (cm) line with anchor statements on the left (no pain) and extreme pain on the right. Pain scores will be determined by measuring the distance in cm from “no pain” to the participant’s anchor point. In this group the score must be “no pain” or 0 cm. Participants randomly assigned to the control group (20 subjects) will first be instructed to complete the VAS for pain with a score less than 4/10 required. Participants randomly assigned to the intervention group (10 subjects) that will receive daily SMS text message reminders for compliance during intervention will first be instructed to complete the VAS for pain with a score less than 4/10 required. Participants randomly assigned to the intervention group (10 subjects) that will not receive daily SMS text message reminders for compliance during intervention will first be instructed to complete the VAS for pain with a score less than 4/10 required.

Next, all participants in all groups will complete 2 self-report questionnaires beginning with the STAI-form Y which is a definitive clinical measure of state and trait anxiety in adults. Form Y has 20 items for assessing trait anxiety and 20 for state anxiety. All items are rated on a 4-point scale (e.g., from “Almost Never” to “Almost Always”). Higher scores indicate greater anxiety.

Next, all participants in all groups will complete the NDI questionnaire which consist of 10 sections (pain intensity, personal care, lifting, work, headaches, concentration, sleeping, driving, reading and recreation) with questions that are measure in a 6-point scale from 0 (no disability) to 5 (full disability). The numeric responses will be added with a score varying from 0-50 where 0 is considered “no activity limitation” and 50 is considered “complete disability.” Furthermore, 0-4 (no disability), 5-14 (mild disability), 15-24 (moderate disability), 25-34 (severe disability) and greater than 35 (complete disability).

Next, all participants in all groups will be familiarized with the Noraxon myoMotion™ system instrument that utilizes inertial measurement units (IMUs) to

measure angles of motion in joints which will measure cervical spine proprioception utilizing the joint position error (JPE) test.

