Participants in the normal group will not receive any interventions in the lab or at home and will not receive education on the use of TENS equipment.

Participants in the control group will not receive any interventions in the lab or at home and will not receive education on the use of TENS equipment.

Participants in the intervention group with daily SMS text message reminders will be provided with a TENS unit by the investigators for home use for a total of 29 days and instructed by a licensed physical therapist for its use and safety. In addition, you will be provided with a daily log sheet to track its use while receiving SMS text message reminders for compliance. Then, the participants in this intervention group will receive a 30-minute high-frequency sensory TENS treatment in lab on the pain site in the neck and upper quadrant area. After the 30-minute high-frequency sensory TENS treatment, the participants in the intervention group will again complete the VAS, STAI, and NDI. Also, cervical spine proprioception will be measured with Noraxon myoMotionTM system instrument utilizing the JPE test.

Participants in the intervention group without daily SMS text message reminders will be provided with a TENS unit by the investigators for home use for a total of 29 days and instructed by a licensed physical therapist for its use and safety. In addition, you will be provided with a daily log sheet to track its use without receiving SMS text message reminders for compliance. Then, the participants in this intervention group will receive a 30-minute high-frequency sensory TENS treatment in lab on the pain site in the neck and upper quadrant area. After the 30-minute high-frequency sensory TENS treatment, the participants in the intervention group will again complete the VAS, STAI, and NDI. Also, cervical spine proprioception will be measured with Noraxon myoMotionTM system instrument utilizing the JPE test.

Session 2 (1st follow up) (Day 8): Participants will return on day eight. Participants in the normal group will be asked to complete again complete the VAS, STAI, and NDI. Also, cervical spine proprioception will be measured with Noraxon myoMotionTM system instrument utilizing the JPE test. Participants will not receive any interventions in the lab.

Participants in the control group will be asked to complete again complete the VAS, STAI, and NDI. Also, cervical spine proprioception will be measured with

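### A 30-minute change in NDI or trait anxiety, measured only in the treated arm, should not be reported as an immediate effect of TENS

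*Protocol*

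**What the plan says.** Objective 1 (Protocol Section 8b) is "To measure the immediate and short-term effects of TENS on subclinical neck or upper quadrant pain with the VAS". The same sentence goes on to anxiety by the STAI, disability by the NDI and proprioception by motion capture. One list of instruments therefore serves both the immediate and the short-term effect.

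Section 8c, First session (Day 1), places the immediate assessment straight after a single lab treatment, in identical words for both intervention subgroups (with and without text reminders): "After the 30-minute high-frequency sensory TENS treatment, the participants in the intervention group will again complete the VAS, STAI, and NDI". The JPE test is repeated as well. For the control group the same section describes no intervention and no second Day 1 assessment.

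Section 8c also describes the instruments. The NDI covers "pain intensity, personal care, lifting, work, headaches, concentration, sleeping, driving, reading and recreation", with each section scored 0 to 5 and the total running from 0 to 50. For the STAI, "Form Y has 20 items for assessing trait anxiety and 20 for state anxiety".

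For the immediate time point the SAP, speaking of the intervention group, says: "we examined changes in outcome variables over time (pre versus post 30 minutes versus post 2 weeks) using repeated measures ANOVA", with Friedman's test as the non-normal alternative. Its list of outcome variables, given earlier in the paragraph, includes anxiety and NDI. It also names the trait score (STAI_T) separately when it reports a baseline difference between groups.

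**The concern.** VAS, state anxiety and joint position error describe the participant at the moment of measurement, so a repeat after 30 minutes is at least aimed at something that can change. Most of the NDI asks about the conduct of daily life, and the trait half of the STAI asks about a general disposition. Nothing in the protocol shortens the question frame for the same-day repeat, limits it to the state items, or says that these values will not be interpreted.

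What is at stake is attribution. If the NDI total or trait score falls between the two Day 1 administrations, the SAP would report a change over time in the treated arm, and Objective 1 supplies the label of an immediate effect on disability or anxiety. The participant has just answered the same questions and knows that a treatment has been given. Without a same-day control repeat, the design offers no means of setting those explanations aside.

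**Working it through.** This is a question of measurement and timing, and no power or sample-size figure decides it. The check is a count of content against the interval.

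**NDI** (Protocol Section 8c)

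- Scale check: 10 sections × 5 points = 50, which agrees with the stated maximum.
- Sections on activities not ordinarily carried out between the two administrations: personal care, lifting, work, sleeping, driving, recreation. That is 6 of 10 sections, and 6 × 5 = 30 of 50 points (60%).
- If reading is also counted: 7 of 10 sections, and 7 × 5 = 35 of 50 points (70%).
- Sections that could plausibly shift within the session: pain intensity, headaches and perhaps concentration. That is at most 3 × 5 = 15 of 50 points (30%). Pain intensity overlaps with the VAS.

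The total is therefore not fixed over 30 minutes, but the part most able to move is symptom content. As an illustration, assume that each of those three sections improves by one step and nothing else changes. The total falls by 3. A participant who starts at 6 ends at 3, and so crosses from the protocol's mild band (5 to 14) to its no-disability band (0 to 4) with no activity section altered.

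**STAI** (Protocol Section 8c)

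- 20 trait + 20 state = 40 items, so 20/40 = 50% concern trait anxiety.
- The whole form is repeated. The frequency-type response anchors given as an example are applied to all items, so they do not by themselves distinguish trait from state. The argument rests on the label of the trait scale.

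**Where the 30-minute value is used**

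| Analysis in the SAP | Groups | Uses the 30-minute value? |
|---|---|---|
| Paired t-test or Wilcoxon, post versus pre | each group separately | not stated; written as a two-point comparison |
| 2x2 mixed ANOVA, two weeks versus pre | intervention and control | no |
| Repeated-measures ANOVA or Friedman, three times | intervention only | yes |

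The three-time analysis is the only one that names the 30-minute value, and it has no control arm. A change there combines any effect of TENS, retest effects and expectation in one quantity, and no second quantity is available to subtract.

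**The case against.** The strongest reply has four parts.

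1. *The documents give no recall period for either instrument, only section names and a trait/state split.* A participant whose pain has eased might reasonably re-rate how limited they feel in lifting or driving, and some NDI sections can move directly. This stands. A reader might infer that the immediate effect on disability and trait anxiety simply cannot be answered, or that any change must be recall or expectation. The documents do not support either statement. What they support is that the sources of a change cannot be told apart.

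2. *The lack of a control repeat affects VAS, state anxiety and JPE just as much.* This also stands, and the remedy has to say so. The difference is one of degree: those measures at least refer to the present moment.

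3. *The main between-group comparison is untouched.* Correct. The 2x2 ANOVA does not use the 30-minute value.

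4. *The SAP is written in the past tense and reports observed baseline differences, so the visit schedule can probably no longer be changed.* This is fair, and it makes the reporting rule the more usable half of the remedy.

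**Conclusion.** The point holds as a limit on interpretation. A pre to post-30-minute change in NDI total or STAI trait score should not be presented as an immediate effect of TENS. It concerns 30 of 50 NDI points (35 if reading is counted) and 20 of 40 STAI items, at one time point, in one within-arm analysis. It does not reach NDI or STAI at the later visits, so the short-term half of Objective 1 is unaffected.

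It rests on two assumptions: that the six activity sections are not exercised during the lab session, and that the SAP's unrestricted reference to outcome variables in the three-time analysis includes NDI and the trait score.

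Two stronger readings are tempting and are not supported.

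- **Loss of power.** A reader might infer that the extra time point costs power on the pre versus follow-up contrast, because three pairs under Bonferroni give 0.05/3 = 0.0167. But the SAP already tests post versus pre separately, with no stated correction, by paired t-test or Wilcoxon. The between-group ANOVA omits the 30-minute value. NDI is compared by medians with Mann-Whitney, so it probably follows the Friedman and Wilcoxon branch, to which Bonferroni is not clearly attached. A power figure would also need a standardised change that the documents do not give; the SAP's only effect size is 0.3, of unstated type.
- **Unequal exposure.** A reader might infer that four questionnaire administrations in the intervention arm against three in the control arm bias the follow-up comparison. The documents give no basis for the direction or size of such a bias.

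**What to change.** **If the Day 1 procedure can still be changed**

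- Protocol Section 8c: limit the post-treatment assessment, in both intervention subgroups, to VAS, the 20 STAI state items and JPE. Give the NDI and the trait items at Day 1 baseline, Day 8 and Day 30 only.
- Protocol Section 8b, Objective 1: state that immediate effects concern pain, state anxiety and proprioception and are uncontrolled within-group changes, while short-term effects concern all outcomes.
- SAP: restrict the pre / 30-minute / follow-up analysis to those three measures, and analyse NDI and STAI_T at baseline and follow-up only. The SAP's two-week follow-up label does not match the protocol's Day 8 and Day 30 visits. That is a separate matter, but it should be settled in the same edit.

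**If the data are already collected**

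- Report the 30-minute NDI and STAI_T values descriptively, without a test and without interpreting them as treatment effects.
- State that this restriction was made after data collection, so that it is not mistaken for selective removal of an outcome.
- Describe the 30-minute changes in VAS, state anxiety and JPE as within-group and uncontrolled.

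**Cost.** The first route is wording in two documents and removes 10 NDI sections + 20 trait items = 30 items from one same-day retest. What is lost is a 30-minute value on two scales that would be hard to interpret. The second route costs a sentence or two in the report. Neither alters the follow-up analyses.

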Noraxon myoMotionTM system instrument utilizing the JPE test. Participants will not receive any interventions in the lab.

Participants in the intervention group with daily SMS text message reminders will be asked to complete again complete the VAS, STAI, and NDI. Also, cervical spine proprioception will be measured with Noraxon myoMotionTM system instrument utilizing the JPE test. Participants will not receive any interventions in the lab.

Participants in the intervention group without daily SMS text message reminders will be asked to complete again complete the VAS, STAI, and NDI. Also, cervical spine proprioception will be measured with Noraxon myoMotionTM system instrument utilizing the JPE test. Participants will not receive any interventions in the lab.

Phone/Email follow up: Participants in the normal, control and intervention (with no SMS text message reminders) groups will be contacted by e-mail and SMS text message during the seventh day period at least one before returning for session two on the eight day and at least three times before returning for the last session on day thirty.

Participants in the intervention group (with SMS text reminders for compliance) will be contacted via SMS text message daily for compliance with high-frequency sensory TENS during the seven-day period before session two and during the twenty-one-day period before last session. We will send a text message to the personal phone. Investigators will be available through phone, text message or email to answer any questions participants may have.

Last session (Day 30): Participants will return on day thirty. Participants in the normal group will be asked to complete again complete the VAS, STAI, and NDI. Also, cervical spine proprioception will be measured with Noraxon myoMotionTM system instrument utilizing the JPE test. Participants will not receive any interventions in the lab and will be given a \$50 gift card.

Participants in the control group will be asked to complete again complete the VAS, STAI, and NDI. Also, cervical spine proprioception will be measured with Noraxon myoMotionTM system instrument utilizing the JPE test. Participants will not receive any interventions in the lab and will be given a \$50 gift card.

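### The TENS subgroup without SMS reminders is still contacted by SMS and e-mail during the compliance period, so Objective 3 does not compare SMS with no SMS

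*Protocol*

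**What the plan says.** Objective 3 (Protocol, section 8.b) reads: "To compare compliance of TENS home usage in groups with and without short message system (SMS), text message, reminders". Section 8.c splits the twenty intervention participants at random into two subgroups of ten. It defines the comparator thus: "ten subjects will receive instructions for home use of TENS without SMS text message reminders". Under the first session, that subgroup takes home a TENS unit for 29 days and a daily log, "to track its use without receiving SMS text message reminders for compliance".

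The phone and e-mail follow-up paragraph of section 8.c then sets out contact between visits:

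- **Subgroup without reminders, together with the normal and control groups:** "Participants in the normal, control and intervention (with no SMS text message reminders) groups will be contacted by e-mail and SMS text message". The frequency is "at least one before returning for session two on the eight day and at least three times before returning for the last session". No content, purpose or maximum is given.
- **Daily-SMS subgroup:** these participants "will be contacted via SMS text message daily for compliance with high-frequency sensory TENS during the seven-day period before session two" and again "during the twenty-one-day period before last session". They are not named among the groups that receive the e-mail contacts.

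**The concern.** Objective 3 needs two subgroups that differ in the reminder and in nothing else that could prompt TENS use. The follow-up paragraph uses the channel under test in the comparator, during the very period over which compliance is recorded. It also gives the comparator e-mails that the daily-SMS subgroup is not scheduled to receive.

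The interpretation of the result is at stake. If a study text or e-mail nudges someone who holds a TENS unit and a log, compliance in the comparator rises and the difference shrinks. A small or absent difference could then mean that reminders do not help, or that a few messages already did part of the work. The design as written could not separate the two.

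**Working it through.** The documents give no effect size, power or sample-size calculation for Objective 3, so there is no stated figure to reproduce. The check is a count of contacts and a comparison of the text for each subgroup.

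**1. Daily-SMS subgroup.** Seven days before session two plus 21 days before the last session: 7 + 21 = 28 texts, expressly for TENS compliance.

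**2. Subgroup without reminders.** At least one contact before Day 8 and at least three before Day 30.
- Counted separately: 1 + 3 = 4.
- If the three include the first: 3.
- Upper limit: none stated.
- Channel: e-mail and SMS. The text does not say whether each contact uses both.

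**3. Relative frequency, if each contact includes a text.** 4 / 28 = 14.3%, or 3 / 28 = 10.7%. The minimum SMS frequency in the comparator is therefore about 11% to 14% of the daily schedule, with e-mail on top.

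**4. Timing.** The follow-up contacts come before the Day 8 and Day 30 visits, so they fall within the 29-day home-use period.

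**5. The two subgroups side by side.**

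| | Daily-SMS subgroup | Subgroup without reminders |
|---|---|---|
| Planned texts | 28 | Occasional: at least 4 contacts (or 3), by e-mail and SMS |
| Stated purpose | TENS compliance | Not stated |
| Scheduled e-mail | Not listed | Yes |
| Maximum | Fixed by the daily schedule | None |

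The subgroups differ in SMS frequency, in SMS purpose and in e-mail contact. Objective 3 names only the presence or absence of SMS reminders.

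**6. Direction and size of any effect.** Let Δ be the compliance difference between daily reminders and no prompting, and let c be the share of that effect that the comparator's contacts produce. The expected difference is then (1 − c) × Δ. If the messages have no prompting effect, c = 0 and nothing is lost. If they prompt TENS use, c > 0 and the difference moves towards zero. Neither c nor Δ is in the documents. The 11% to 14% in step 3 is a ratio of message counts, not an estimate of c.

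**The case against.** The strongest reply is that these are ordinary visit contacts. The same contact goes to the normal and control groups, and for the control group the protocol states: "Participants in the control group will not receive any interventions in the lab or at home". A message common to people with no TENS unit can hardly be a TENS reminder. The contacts are timed to the return visits, and only the daily-SMS paragraph mentions compliance. Elsewhere in section 8.c the comparator is mostly described as lacking daily reminders, in places with the qualifier that these are for compliance. Occasional follow-up contact is compatible with that description, and no section promises an arm free of all SMS.

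Most of this stands. A reader might infer that the comparison is contaminated by design, or that a definite amount of power is lost. The documents support neither. They do not show that the messages mention TENS use, and any power loss would rest on an assumed effect and an assumed dilution, which could be zero.

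It is also fair to say that ten against ten is a small comparison that would leave a null result hard to interpret in any case. Neither section 11 of the protocol nor the SAP gives an analysis for Objective 3. Dilution towards zero would not by itself undermine a positive finding.

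What the reply does not remove: nothing excludes TENS content from messages to the ten people who hold a unit and a log, no maximum is set, and the subgroups differ in e-mail contact as well as in daily texts. If daily against occasional contact is what is meant, Objective 3 does not say so.

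**Conclusion.** The point holds as a mismatch between Objective 3 and the follow-up procedure. The contrast as written is 28 daily compliance texts against at least 4 contacts (3 if cumulative) by SMS and e-mail, of unspecified content and without an upper limit. Contamination of the comparator is possible. It would usually bias the compliance difference towards zero, on the assumption that any prompting effect of the extra contacts raises TENS use in the comparator. Its size cannot be computed from the documents, and no power figure should be attached to it.

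The textual mismatch is certain; whether it has any effect is not. This is a cheap improvement to the interpretability of one of the three stated objectives. It does not bear on the comparison of TENS with control.

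**What to change.** Amend the follow-up paragraph of Protocol section 8.c:

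1. Contact the intervention subgroup without reminders by e-mail or phone only, with content restricted to visit scheduling and no mention of TENS use or the log.
2. Give the daily-SMS subgroup the same scheduling contacts, by the same route and in the same fixed number, so that the two subgroups differ only in the daily compliance text.
3. Log the date and route of every contact in both subgroups.

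If the investigators prefer to keep SMS for scheduling, they should restate Objective 3 as daily compliance SMS against infrequent follow-up contact, and interpret the result in those terms.

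The cost is a one-paragraph edit and a simple contact log, with no added visits or participants. The downside is a slightly weaker prompt to attend visits in about ten participants, and this subgroup would no longer share its contact route with the normal and control groups.
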